#### **5.2.2.3. Geometric Mean Fold Rises**

The GMFRs will be calculated by exponentiating the mean difference of logarithmically transformed assay results (later minus earlier). The associated 2-sided 95% CIs are computed by exponentiating the limits of the CIs obtained using Student's t-distribution for the mean difference on the natural log scale.

CCI [REDACTED]

[REDACTED]

### 5.3. Methods to Manage Missing Data

A partial AE start date (missing day, missing both month and day) will be imputed by assigning the earliest possible start date using all available information, such as the stop date of the AE and the vaccination date(s) from the same participant, following the Pfizer standard of handling incomplete AE start date. A complete missing start date for an AE is not allowed in the data collection.

The LLOQ for each assay will be provided by Vaccines Research and Development as part of the electronic data transfer or within the Clinical Testing Completion Memo prior to statistical analysis. Assay results above the LLOQ will be reported, and values below the LLOQ, denoted as BLQ, will be set to  $0.5 \times \text{LLOQ}$  for analysis.

No additional imputation will be applied to other missing data.

## 6. ANALYSES AND SUMMARIES

### 6.1. Primary Endpoint(s)

#### 6.1.1. Primary Safety Endpoint(s)

##### 6.1.1.1. Local Reactions

Results from local reactions after each dose (Dose 1, Dose 2, Dose 3, and Dose 4) will be summarized separately.

##### 6.1.1.1.1. Main Analysis

- Estimand: The percentage of participants reporting prompted local reactions (redness, swelling, and pain at the injection site) within 7 days after each dose ([Section 2.1](#)).
- Analysis set: Safety population ([Section 4](#)).
- Analysis time point: Within 7 days after each dose.
- Analysis methodology: The between-group difference (20vPnC SC group – 13vPnC SC group, or 20vPnC IM group – 20vPnC SC group) and the corresponding 2-sided 95% CI will be calculated using the Miettinen and Nurminen method ([Section 5.2.1](#)) for each reaction.
- Intercurrent events and missing data: Missing values will not be imputed. Confirmed e-diary errors will be excluded from the analysis.

- Reporting results: Count and percentage of participants with the indicated endpoint and the associated 2-sided 95% CI for each and any local reaction after each dose in each vaccine group will be presented by maximum severity across severity levels. Between-group differences (20vPnC SC group – 13vPnC SC group, or 20vPnC IM group – 20vPnC SC group) in these percentages and their 2-sided 95% CIs will also be provided. The denominator used in the percentage calculation will be the number of participants with any e-diary data reported after the specified vaccination.

CCI [REDACTED]

[REDACTED]

[REDACTED]

[REDACTED]

[REDACTED]

[REDACTED]

[REDACTED]

[REDACTED]

[REDACTED]

[REDACTED]

[REDACTED]

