## 9.4. Statistical Analyses

The SAP will be developed and finalized before database lock for any of the planned analysis in [Section 9.5](#). The SAP will describe the participant populations to be included in the analyses, and procedures for accounting for missing, unused, and spurious data. This section is a summary of the planned statistical analyses of the primary, secondary, CCI [REDACTED] endpoints.

All CIs in the statistical analysis will be calculated as two-sided at 95% level.

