#### 9.4.2. Safety Analyses

Endpoint	Statistical Analysis Methods
Primary	
 
• Descriptive statistics will be provided for each reactogenicity endpoint for each dose and vaccine group. Local reactions and systemic events from Day 1 through Day 7 after each vaccination will be presented by severity cumulatively across severity levels. Descriptive summary statistics will include counts and percentages of participants with the indicated endpoint and the associated Clopper-Pearson 95% CIs. Between-group differences (20vPnC SC – 13vPnC SC and 20vPnC IM – 20vPnC SC) in percentage and 2-sided 95% CIs will be provided. The Miettinen and Nurminen method will be used to derive the 95% CI for the difference in percentages between vaccine groups.
 
• AEs will be categorized according to Medical Dictionary for Regulatory Activities (MedDRA) terms. A 3-tier approach will be used to summarize AEs. Under this approach AEs are classified into 1 of 3 tiers: (1) Tier 1 events are prespecified events of clinical importance and are identified in a list in the product’s safety review plan; (2) Tier 2 events are those that are not Tier 1 but are considered “relatively common”; a MedDRA preferred term is defined as a Tier 2 event if there are at least 4 of participants in at least 1 vaccine group reporting the event; and (3) Tier 3 events are those that are neither Tier 1 nor Tier 2 events. For both Tier 1 and Tier 2 events, the 95% CIs for the difference in percentage of participants reporting the events between 20vPnC SC and 13vPnC SC groups, or 20vPnC IM and 20vPnC SC groups will be calculated using the Miettinen and Nurminen’s method. In addition, for Tier 1 events, the asymptotic p-values will also be presented for the difference in percentage of participants reporting the events, based on the same test statistic and under the assumption that the test statistic is asymptotically normally distributed. There is no Tier 1 event identified for 20vPnC at this stage. Descriptive summary statistics (counts and percentages and associated Clopper-Pearson 95% CIs) will be provided for Tier 3 events for each vaccine group.
 
• SAEs and NDCMCs will be categorized according to MedDRA terms. Counts, percentages and the associated Clopper-Pearson 95% CIs of SAEs and NDCMCs from Dose 1 to 1 month after Dose 4 will be provided for each vaccine group.
 

Endpoint	Statistical Analysis Methods

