## 2.2. Study Design

This Phase 3, multicenter, randomized, double-blind, third-party-unblind study will be conducted at investigator sites in Japan. CCI

The purpose of this study is to describe safety and conduct the pivotal immunogenicity comparison of 20vPnC administered by SC injection to the licensed pneumococcal conjugate vaccine, 13vPnC (ie, Prevenar 13®), administered by the currently indicated SC injection in infants CCI. Data will also be generated on 20vPnC administered by IM injection, with the 20vPnC administered by SC injection as a control.

Approximately 666 infants 2 through 6 months of age at the time of consent, by their parent(s)/legal guardian(s), will be enrolled into the study. Participants will be randomized equally to one of the following vaccine groups: (1) 20vPnC SC group, (2) 13vPnC SC group (control vaccine), or (3) 20vPnC IM group. Participants will receive the same vaccine (20vPnC or 13vPnC) by the same injection method (SC or IM injection) for all 4 doses at Visits 1, 2 (4 to 8 weeks after Visit 1), 3 (4 to 8 weeks after Visit 2), and 5 (12 to 15 months of age with  $\geq 60$  days after Dose 3). All vaccine groups will be blinded to all members of the site involved in the study except unblinded site staff who will administer 20vPnC or 13vPnC.

As this study is the first study where 20vPnC is administered subcutaneously and the study participants are infants, a daily enrollment limit of  $\leq 5$  participants will be in place from study start until the study has accumulated safety data from 45 participants through 7 days of follow-up after Dose 1. These data will be carefully monitored and reviewed by the study team. If there are no safety signals in the first 45 participants after Dose 1, the daily enrollment limit will be removed.

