**Table 3. Grading Scales for Local Reactions**

Local Reaction	GRADE 1 Mild	GRADE 2 Moderate	GRADE 3 a Severe	GRADE 4 b
Redness	1 to 4 caliper units (or measuring device units) = >0 to 2.0 cm	5 to 14 caliper units (or measuring device units) = >2.0 to 7.0 cm	>14 caliper units (or measuring device units) = >7.0 cm	Necrosis or exfoliative dermatitis
Swelling	1 to 4 caliper units (or measuring device units) = >0 to 2.0 cm	5 to 14 caliper units (or measuring device units) = >2.0 to 7.0 cm	>14 caliper units (or measuring device units) = >7.0 cm	Necrosis
Pain at injection site (tenderness)	Hurts if gently touched (eg, whimpers, winces, protests, or withdraws)	Hurts if gently touched with crying	Causes limitation of limb movement	Emergency room visit or hospitalization for severe pain (tenderness) at injection site

Abbreviation: CRF = case report form.

**Note:** If the size of the redness and/or swelling falls between 2 measuring device units, the higher measuring device unit number will be recorded in the e-diary.

- a. Parents/legal guardians of the participants experiencing local reactions >14 caliper units (>7.0 cm) are to be contacted by the study site. An unscheduled visit may be required.
- b. Grade 4 assessment should be made by the investigator. Grade 4 will not be collected in the e-diary but will be collected as an AE on the CRF. The severity of the local reaction should be graded using the AE grading scale.

For each local reaction after each dose, the maximum severity grade will be derived for the e-diary collection period (Day 1 through Day 7, where Day 1 is the day of each dose) as follows:

maximum severity grade = highest grade (maximum severity) within 7 days after vaccination (Day 1 through Day 7) among severity grades reported for that local reaction in the e-diary.

CCI [Redacted]

[Large Redacted Block]

[Redacted]

[Redacted]

CCI

[Redacted]

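### Severity rows for local reactions and systemic events: cumulative in the protocol, by maximum severity with between-group intervals in the SAP, so that an exclusive mild row can point the wrong way

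*SAP*

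**What the plan says.** **Protocol 9.4.2.** "Local reactions and systemic events from Day 1 through Day 7 after each vaccination will be presented by severity cumulatively across severity levels". The same paragraph plans between-group differences (20vPnC SC minus 13vPnC SC, and 20vPnC IM minus 20vPnC SC) with Miettinen-Nurminen 95% CIs.

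**SAP 6.1.1.1.1 (local reactions).** Counts, percentages and CIs for each reaction and for any reaction, after each dose, "in each vaccine group will be presented by maximum severity across severity levels". The next sentence says that between-group differences "in these percentages and their 2-sided 95% CIs will also be provided". SAP 6.1.1.2.1 uses the same wording for systemic events. The word for cumulative appears in neither section.

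**SAP 3.1.1.1, below Table 3.** The grade is one value per infant, reaction and dose: "maximum severity grade = highest grade (maximum severity) within 7 days after vaccination (Day 1 through Day 7"). For fever, SAP 3.1.1.2 maps the maximum temperature into the four bands of Table 5, which do not overlap.

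**Common ground.** In both documents the intervals are two-sided 95% and the method is Miettinen-Nurminen. The SAP methodology bullet also gives a difference for each reaction as such, and the estimand is the percentage with the reaction at all. The Protocol synopsis describes the safety evaluation as descriptive.

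**The concern.** If each infant is counted once, at the highest grade, the mild row holds infants whose worst reaction was mild. That percentage can fall because fewer infants reacted, or because the same infants reacted more strongly. The moderate row has the same defect one step up: if as many infants leave it for severe as enter it from mild, it does not move. A cumulative row (any, moderate or worse, severe) reads in one direction only, because more or stronger reactions cannot lower it.

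These are primary safety tables, and the Protocol risk assessment states that this is the first study to give 20vPnC subcutaneously. An interval on the mild row that excludes zero in favour of the more reactogenic vaccine would be an avoidable misreading. In addition, a programmer who follows the SAP and one who follows the protocol could produce different tables.

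**Working it through.** **Inputs.** There are 222 infants per group (666 randomized equally to three groups, 666/3 = 222; also the N of Protocol Table 7). This is the maximum, since the SAP denominator is infants with e-diary data after the dose. The intervals are Miettinen-Nurminen, two-sided 95%. Neither document gives reaction rates by grade, so the rates below are assumptions and are varied.

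**The plan's own figure.** Protocol Table 7 is the only stated safety calculation. The probability of at least one event is 1 − (1 − p)^222, which gives 67.1%, 89.3% and 96.5% for p = 0.5%, 1.0% and 1.5%. The table states 67%, 89% and 97%, so it is reproduced. The documents state no figure for differences by severity.

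**Formula.** For a difference δ, z(δ) = (p1 − p2 − δ)/√V(δ), where V(δ) = [p̃1(1 − p̃1)/n1 + p̃2(1 − p̃2)/n2] × N/(N − 1), N = n1 + n2, and p̃1, p̃2 are the maximum-likelihood proportions under p1 − p2 = δ. The limits are the values of δ at which z = ±1.96.

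**Example.** Control: 89 mild, 40 moderate, 4 severe of 222 (about 40%, 18% and 2%). Test vaccine: 22 infants move from mild to moderate, giving 67, 62 and 4. The total with any reaction is 133 in both groups.

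| Row | Test v control | Difference, points (95% CI) |
|---|---|---|
| Exclusive: mild | 67 v 89 | −9.9 (−18.7 to −1.0) |
| Exclusive: moderate | 62 v 40 | +9.9 (2.1 to 17.7) |
| Exclusive: severe | 4 v 4 | 0.0 (−3.0 to 3.0) |
| Cumulative: any | 133 v 133 | 0.0 (−9.1 to 9.1) |
| Cumulative: moderate or worse | 66 v 44 | +9.9 (1.9 to 17.9) |
| Cumulative: severe | 4 v 4 | 0.0 (−3.0 to 3.0) |

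Hand check of the mild row with the simple Wald interval: SE = √[(0.3018 × 0.6982 + 0.4009 × 0.5991)/222] = 0.0451, so −9.9 ± 1.96 × 4.51 gives −18.7 to −1.1, close to the score interval.

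**How large must the shift be?** With 40% mild in the control group:

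- 5-point shift: −5.0 (−13.9 to 4.1)
- 8-point shift: −8.1 (−16.9 to 0.8)
- 15-point shift: −14.9 (−23.4 to −6.2)

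The smallest shift at which the mild interval excludes zero:

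| Control mild | Infants moved | Difference, points (95% CI) |
|---|---|---|
| 10% (22) | 11 | −5.0 (−10.2 to −0.1) |
| 20% (44) | 16 | −7.2 (−14.1 to −0.3) |
| 30% (67) | 19 | −8.6 (−16.7 to −0.4) |
| 40% (89) | 20 | −9.0 (−17.8 to −0.1) |
| 50% (111) | 21 | −9.5 (−18.6 to −0.2) |

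**How often?** For a true fall in the mild row from 40% to 30%, the normal approximation gives Φ[(0.10 − 1.96 × √(2 × 0.35 × 0.65/222))/√((0.40 × 0.60 + 0.30 × 0.70)/222)] = Φ[(0.10 − 0.0887)/0.0450] = Φ(0.25), or about 60%.

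**The case against.** The case for leaving the SAP alone has several parts, and much of it stands.

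- **The worsening is visible.** A reader might infer that the SAP table would hide a more reactogenic vaccine. It would not. In the example the moderate row rises by 9.9 points with an interval above zero, directly below the mild row.
- **No information is lost.** A reader might also infer that a moderate-or-worse interval is out of reach. If the rows are exclusive, their counts add (62 + 4 = 66, 40 + 4 = 44), and the method needs only n and N. The SAP simply does not commit to reporting that interval.
- **The reversal is not automatic.** It needs the shifts shown above, and even a true 10-point fall from 40% produces it only about 60% of the time. No hypothesis test is planned on any severity row, so to speak of significantly fewer mild reactions would overstate a descriptive interval that excludes zero.
- **The wording is loose on both sides.** A cumulative table can also be built from each infant's highest grade, the SAP does not expressly say that its rows are exclusive, and the protocol does not define its cumulative presentation. This stands in part: the exclusive reading is the natural one, not the only one. That ambiguity is itself a reason to clarify.
- **Fever bands do not overlap in the protocol either** (Protocol Table 4). That is true, but Protocol 9.4.2 applies its cumulative sentence to systemic events, which include fever, and the lower bounds of the bands supply the thresholds.
- **The SAP may modify the protocol.** Protocol Section 9 allows this and reserves an amendment for major modifications of primary endpoint definitions or their analyses. The documents do not support a claim that this change needed one. The SAP version history is not in the text available here, and blocks after both analyses are blacked out, so an explanation or a supplementary table may exist.

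**Conclusion.** The point holds as a protocol-SAP inconsistency in a primary safety table, together with a row that can mislead. On the natural reading of the SAP, the mild row can favour the more reactogenic vaccine with a 95% CI below zero, for mild-to-moderate shifts of about 5 to 9.5 points at 222 per group. This rests on assumed control mild rates of 10% to 50%, on e-diary data from all 222 infants, and on exclusive rows. Total reactions and severe reactions are held equal in the worked example.

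It goes no further. The any-grade comparison, which matches the estimand, is the same under either presentation. The higher-grade row still shows the harm, and the trial's conclusions are not at stake. The change is worth making because it costs almost nothing and makes every row with an interval readable in one direction.

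**What to change.** In SAP 6.1.1.1.1 and 6.1.1.2.1, state that percentages, between-group differences and Miettinen-Nurminen 95% CIs are given for cumulative categories:

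- local reactions and systemic symptoms: any grade, moderate or worse, severe;
- fever: from the lower bound of each existing band upward (≥37.5, >38.4, >38.9 and >40.0°C).

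Keep the maximum-severity rows as a descriptive breakdown by count and percentage. If the sponsor prefers intervals on the maximum-severity rows, the SAP should say that those rows are exclusive and document why it departs from Protocol 9.4.2.

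The cost is a few sentences in the SAP and a revised table shell. No new data are needed, since the grades and temperature cut-points are already defined.

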### 6.1.1.2. Systemic Events

Results from systemic events after each dose (Dose 1, Dose 2, Dose 3, and Dose 4) will be summarized separately.

#### 6.1.1.2.1. Main Analysis

- Estimand: The percentage of participants reporting prompted systemic events (fever, decreased appetite, irritability, and drowsiness/increased sleep) within 7 days after each dose ([Section 2.1](#)).
- Analysis set: Safety population ([Section 4](#)).
- Analysis time point: Within 7 days after each dose.

- Analysis methodology: The between-group difference (20vPnC SC group – 13vPnC SC group, or 20vPnC IM group – 20vPnC SC group) and the corresponding 2-sided 95% CI will be calculated using the Miettinen and Nurminen method (Section 5.2.1) for each event.
- Intercurrent events and missing data: Missing values will not be imputed. Confirmed e-diary errors will be excluded from the analysis.
- Reporting results: Count and percentage of participants with the indicated endpoint and the associated 2-sided 95% CI for each and any systemic event after each dose in each vaccine group will be presented by maximum severity across severity levels. Between-group differences (20vPnC SC group – 13vPnC SC group, or 20vPnC IM group – 20vPnC SC group) in these percentages and their 2-sided 95% CIs will also be provided. The denominator used in the percentage calculation will be the number of participants with any e-diary data reported after the specified vaccination.

CCI

[REDACTED]

[REDACTED]

[REDACTED]

[REDACTED]

[REDACTED]

[REDACTED]

[REDACTED]

[REDACTED]

[REDACTED]

[REDACTED]

[REDACTED]

[REDACTED]

### 6.1.1.3. Adverse Events

#### 6.1.1.3.1. Main Analysis

- Estimands:
  - The percentages of participants reporting AEs from Dose 1 to 1 month after Dose 3 (Section 2.1).

- The percentages of participants reporting AEs from Dose 4 to 1 month after Dose 4 (Section 2.1).
- Analysis set: Safety population (Section 4).
- Analysis time points: Dose 1 to 1 month after Dose 3 and Dose 4 to 1 month after Dose 4.
- Analysis methodology: 3-Tiered approach as described in Section 5.2.1.
- Intercurrent events and missing data: No missing values will be imputed except for partial AE start dates (Section 5.3).
- Reporting results: For all 3 tiers, the numerator (n) and the denominator (N) used in the percentage calculation, the percentage (%), and the corresponding 2-sided 95% CI for participants reporting any AE, each system organ class, and each preferred term within system organ class will be presented by vaccine group.
- In addition, for AEs classified as Tier 2 events, the differences in percentages and associated 2-sided 95% CIs (20vPnC SC group – 13vPnC SC group, or 20vPnC IM group – 20vPnC SC group) will be provided.
- Further, for Tier 1 events, if any are identified, the difference in percentages, the associated 2-sided 95% CI for the risk difference, and the asymptotic p-values will also be provided.

CCI [REDACTED]

[REDACTED]

[REDACTED]

[REDACTED]

[REDACTED]

[REDACTED]

[REDACTED]

#### 6.1.1.4. Serious Adverse Events and Newly Diagnosed Chronic Medical Conditions

##### 6.1.1.4.1. Main Analyses

- Estimands:
  - The percentage of participants reporting SAEs from Dose 1 to 1 month after Dose 4 ([Section 2.1](#)).
  - The percentage of participants reporting NDCMCs from Dose 1 to 1 month after Dose 4 ([Section 2.1](#)).
- Analysis set: Safety population ([Section 4](#)).
- Analysis time point: Dose 1 to 1 month after Dose 4.
- Analysis methodology: Descriptive statistics.
- Reporting results: The numerator (n) and the denominator (N) used in the percentage calculation, the percentage (%), and the corresponding 2-sided 95% CI for participants reporting any SAEs/NDCMCs, each system organ class, and each preferred term within system organ class will be presented by vaccine group. SAEs and NDCMCs will be presented separately.

CCI

#### 6.1.2. Primary Immunogenicity Endpoints

##### 6.1.2.1. Participants With Predefined Pneumococcal Serotype-Specific IgG Concentrations at 1 Month After Dose 3

###### 6.1.2.1.1. Main Analysis

- (For 20vPnC SC) Estimands:
  - For each of the 13 matched serotypes in 20vPnC, the difference in percentages of participants with predefined serotype-specific IgG concentrations between the 20vPnC SC group and the 13vPnC SC group ([Section 2.1](#)).

- For each of the 7 additional serotypes in 20vPnC, the difference in the percentages of participants with predefined serotype-specific IgG concentrations between the 20vPnC SC group and the lowest percentage of participants with predefined serotype-specific IgG concentrations among the 13 serotypes from the 13vPnC SC group, excluding serotype 3.
- (For 20vPnC IM) Estimand: For each of the 20 serotypes in 20vPnC, the difference in percentages of participants with predefined serotype-specific IgG concentrations between the 20vPnC IM group and the 20vPnC SC group ([Section 2.1](#)).
- Analysis set: Dose 3 evaluable immunogenicity population ([Section 4](#)).
- Analysis time point: 1 Month after Dose 3.
- Analysis methodology: The between-group difference (20vPnC SC – 13vPnC SC and 20vPnC IM – 20vPnC SC) and the corresponding 2-sided 95% CI will be calculated using the Miettinen and Nurminen method ([Section 5.2.1](#)) for each serotype. NI of 20vPnC SC relative to 13vPnC SC will be assessed by comparing the lower bound of the 95% CI for the between-group difference ([Section 5.1.1.1](#)).
- Intercurrent events and missing data: Serology data deemed unevaluable because of noncompliance with the key protocol criteria will be excluded. Missing data will not be imputed.
- Reporting results: For each of the 20 vaccine serotypes, the numerator (n), the denominator (N) used in the percentage calculation, the percentage (%), and the corresponding 2-sided 95% CI for participants with predefined IgG concentrations from each vaccine group, as well as the percentage difference and the associated 95% CI, will be presented.

